# 8. Subject selection

# 8.1. Study population

The sample size will be approximately 1000 subjects who must be enrolled over the two-year period, based on the annual rate of cryoballoon ablations carried out in Spain.

All local and regional regulatory requirements must be met before the activation of each site and before the enrollment of subjects in the study. Each participating site should have the official confirmation from the sponsor authorizing them to start any study activity. Enrollment will last for 2 years. It is expected to commence in May 2016 and finish in May 2018.

A subject will be considered to be enrolled in the observational study from the moment in which he/she signs the Data Release Form for the study.

The investigator will keep a register of all the subjects enrolled in the study, linking each subject to a specific identification code for that site and that subject. This code will be assigned automatically by the electronic Case Report Form and will not contain any of the subject's personal information, so that the anonymity of the participating subjects is assured.

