#### Annual follow-up (+/- 28 days):

5.- Variables during follow-up: anti-arrhythmic treatment, clinical recurrence of arrhythmia, result of the continuous ECG monitoring, 12-lead ECG, Nuubo monitoring method, etc. according to the protocol for each site.

A blanking period of 3 months has been established.

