  - Congestive heart failure
  - Hemorrhagic events without stroke
  - Myocardial infarction
  - Stroke
  - Arrhythmia: atrial flutter or inappropriate sinus tachycardia or sinus dysfunction after the blanking period
  - Recurrence of AF or left flutter after the blanking period

Note: The cases of recurrence of AF and the hospitalizations arising from AF will be collected in the adverse event form even though they will be processed as part of the analysis of the efficacy and not safety variables.

The investigator has to specify on the eCRF whether an adverse event can be deemed to be serious or not. If the adverse event meets any of the following criteria, it is considered a serious adverse event (SAE):

- Led to death
- Caused serious deterioration in the subject's health that has:
  - a) resulted in a life-threatening illness or injury, or
  - b) resulted in a permanent impairment of a body structure or a body function, or
  - c) required in-subject hospitalization or prolongation of existing hospitalization, or
  - d) resulted in medical or surgical intervention to prevent life threatening illness or injury or permanent impairment to a body structure or a body function.

Note: Planned hospitalization for a pre-existing condition is not considered a serious adverse event.

Note 2: Hospitalization is defined as patient staying overnight at the hospital (more than 24h)

The investigator also has to evaluate on the eCRF whether there is a reasonable possibility that the device may have caused or contributed to an AE. The factors that could be considered are time relationships, biological plausibility, the association (or lack of association) with the underlying disease and the presence (or absence) of a more likely cause. If an adverse event is classiffied as potentially related to the device this should be also notififed following the regular communication channels of the vigilance system.

All the data collected relating to adverse events will be reviewed remotely to ensure the correct reporting and classification of the event. In the event of having doubts about the classification and relationship with the device established by the investigator, the Scientific Committee will be consulted.

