# 13. Statistical design and methods

The following statistical analysis plan of the data will be carried out:

The variables analyzed will be those collected in the subject registry corresponding to the different protocols of the procedure, intervention data, complications, follow-up and long-term results in these subjects. In the Method section there is a list of variables of interest.

Recurrence of AF will be defined as a clinically diagnosed episode of AF and accordingly documented (on ECG, Holter monitor with a duration of at least 30 seconds or implantable devices or event recording systems).

It is expected to carry out 3 analyses of the primary and secondary objectives described in the Clinical Investigation Plan:

- 1. At the end of the first year of enrollment
- 2. At the end of the second year of enrollment
- 3. At the end of follow-up

On the other hand, there will be 4 analyses of additional proposals throughout the study (see Appendix B: Publications Plan)

- Two analyses at the end of enrollment.
- Two analyses at the end of follow-up.

Each of the variables of interest will be described univariantly and individually.

Crosses of variables will also be carried out to describe each one of the clinical strata of interest.

When it is possible and of interest for the investigators, statistical comparisons between strata will be carried out through statistical tests.

Specific statistical models to respond to the interests of the investigators will be proposed, such as comparison of the procedures or comparison of subject strata.

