## 13.1. Analysis of clinical data

It is expected to include approximately 1000 subjects enrolled at approximately 30 Spanish sites, with an enrollment period of 2 years and a follow-up period of one year from the time of enrollment of each subject. The subjects analyzed will be the ones included in the RECABA study database: "Spanish Registry of Cryoballoon Ablation". The variables analyzed will be those mentioned previously with the intention of adequately describing the activity of the clinical sites, the procedures used and the diseases treated in accordance with standard clinical practice.

All the data are anonymized in origin so that it is not possible to identify the subjects.

The collection of data will be prospective from the time of enrollment.

The database will be received codified and debugged, and the allocation of the lost values that have been decided previously.

The basic report at the end of enrollment and at the end of the follow-up period will consist of: The quantitative variables are expressed as mean, median, typical deviation and interquartile range depending on which is most suitable for the distribution of values. The differences between groups in relation to the quantitative variables will be evaluated through the student t test for independent samples or the analysis of variance (depending on the number of groups compared) and between variables through the student t test for related samples or the analysis of variance of repeated measures, as applicable. To analyze the relationships between categorical variables the chi-squared test ( $\chi^2$ ) and the Fisher's exact test will be used. The differences of proportions will be assessed through the homogeneity test  $\chi^2$ . To assess the relationships between the quantitative variables the Pearson or Spearman r correlation will be used, as appropriate.

The intermediate statistical reports proposed by the investigators will depend on the hypotheses suggested by the investigator. They will include at least a descriptive analysis such as the one described previously. In addition, the appropriate models to respond to the hypotheses proposed will be estimated, which can include techniques of the style of exploratory factor analysis, analysis of multiple contingency, analysis of logistical regression, analysis of conglomerates or analysis of multifactorial variance.

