## **Follow-up**

The Follow-up table contains clinical information related to the follow-up of the patient. At the time of writing this protocol, it is unknown whether a patient can have multiple follow-up visits.

Continuous variables will be described using the statistics of central tendency (mean and median), dispersion (minimum, maximum, standard deviation and interquartile range) and shape (skewness and kurtosis). The number of valid cases and the number of cases with missing values will be reported. The continuous variables in this table are: Date of the follow-up visit, Date of post-procedure discharge, Date of admission, Date of discharge, Number of hospital stays.

The categorical variables will be described by frequencies and percentages. The number of valid cases and the number of cases with missing values will be reported. The categorical variables contained in this table are: Follow-up visit, ECG record / Monitoring type, Recurrence 3 months post-procedure, Recurrence specification, Asymptomatic AF, Treatment, Antiarrhythmics, Antiarrhythmic type, Specify, Anticoagulants, NACOs type, REDO, Type REDO, Death, Hospital stay

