### **Statistical models**

In order to conclude on the primary objective of the study, the number and percentage of cases with absence of atrial fibrillation recurrences will be calculated after 12 months of follow-up, after the cryoablation procedure. The scientific coordinators of the study will have to determine the closing date of the database so that it has been possible to collect information from 12 months of follow-up of a sufficiently large number of patients.

The protocol defines AF recurrence as a clinically diagnosed and documented episode of AF (using ECG, Holter monitor with a duration of at least 30 seconds, or using implantable devices

or event monitoring systems). The information necessary to determine the existence of a recurrence of AF will be extracted from the Follow-up and Adverse Events tables.

The existence of differences between patients with and without recurrence in clinical variables and patient follow-up will be explored. Student's t statistics (for continuous variables) and  $\chi^2$  (for categorical variables) will be used. If there are appreciable differences between the groups of patients in the clinical variables, logistic regression models will be proposed to study the multivariate effect of the variables and assess their predictive capacity.

The waiting times until the moment of recurrence of AF will be described using survival models (survival tables and Kaplan-Meier) and the existence of variables capable of predicting the differences between both groups of patients will be explored.

The necessary statistical analyzes will be approached to verify the secondary objectives based on the variables designated by the study coordinators.

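### Carrying the last status forward to database closure can count subjects without 12 months of follow-up as AF-free

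*SAP*

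**What the plan says.** **Outcome.** SAP, Statistical models, answers the primary objective with the number and percentage of subjects without AF recurrence, "after 12 months of follow-up, after the cryoablation procedure". It adds survival tables and Kaplan-Meier for time to recurrence and states no censoring rule.

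**Missing status.** SAP, Treatment of missing values, starts from MCAR, handled variable by variable. For consecutive measurements, or where elapsed time matters, it carries the last value forward. Its example is event status: a subject who has had no event, or for whom nothing is known, at database closing is taken to be as at the last valid measurement.

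**Timing.** SAP, Statistical models, leaves the closing date to the scientific coordinators. They must have 12-month information on enough patients, and no number is set. Protocol section 13 lists analyses of the primary objective at the end of enrollment year 1, at the end of enrollment year 2 and at the end of follow-up.

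**Blanking.** Protocol section 9.1, under annual follow-up, says "A blanking period of 3 months has been established". Section 11.2 lists "Recurrence of AF or left flutter after the blanking period" among the events to collect. The definition in section 13 ("Recurrence of AF will be defined as a clinically diagnosed episode of AF and accordingly documented") gives no start time. The SAP repeats it without one ("The protocol defines AF recurrence as a clinically diagnosed and documented episode of AF"). The SAP's Follow-up table contains "Recurrence 3 months post-procedure, Recurrence specification".

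**Clock.** Protocol section 13.1 plans "a follow-up period of one year from the time of enrollment of each subject". Section 8.1 counts a subject as enrolled "from the moment in which he/she signs the Data Release Form for the study". The SAP counts from the procedure.

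**The concern.** Recurrence and freedom from recurrence are not recorded alike. A recurrence can enter the database when it happens, as an adverse event (Protocol section 11.2). Freedom from AF at 12 months is established only by the annual follow-up, the one point in Protocol Table 1 at which AF monitoring is scheduled. If subjects without that follow-up keep an earlier AF-free status, any recurrence after their last contact is counted as a success. The error runs one way: carry-forward cannot give a lower AF-free figure than complete follow-up would.

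The same rule affects the Kaplan-Meier analysis. A subject last seen free of AF at month 4 would stay in the risk set, event-free, until closure, and the curve would sit too high.

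The primary result is one descriptive percentage with no comparator, so a shift in it goes straight into the registry's main conclusion. The blanking and clock gaps add to the problem, because two analysts could count different episodes over different intervals.

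**Working it through.** **1. Inputs.** About 1000 subjects (Protocol section 8.1), 2 years of enrollment and 1 year of follow-up (section 6.1), a ±28-day visit window and 3 months of blanking (section 9.1). The documents give no expected AF-free rate, loss to follow-up or wait from consent to procedure. Every value of these below is an assumption.

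**2. Yardstick.** The largest 95% half-width at n = 1000 is 1.96 × √(0.25/1000) = 3.1 points, or 31 subjects.

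**3. Final analysis.** Let L be the share with neither a recurrence nor a 12-month assessment, and p the AF-free share among the rest. If all of L have an earlier AF-free status to carry:

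- available-case percentage = p
- carry-forward percentage = p(1 − L) + L = p + L(1 − p)
- difference = L(1 − p)

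| Assumed L | p = 60% | p = 75% | p = 90% |
|---|---|---|---|
| 5% | +2.0 | +1.25 | +0.5 |
| 10% | +4.0 | +2.5 | +1.0 |
| 20% | +8.0 | +5.0 | +2.0 |

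These are upper limits for each L. If only a fraction f of L has a status to carry and the others drop out, the difference is fL(1 − p)/(1 − L + fL). This rises with f and reaches L(1 − p) at f = 1.

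**4. Kaplan-Meier.** If every subject without an event is carried to a closure at least 12 months after the procedure, nobody is censored before 12 months. The estimate then equals the carry-forward percentage in step 3, so the curve is no independent check.

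**5. Analyses during enrollment.** At the end of year 1 essentially no subject can have 12 months after the procedure. Even counting from the opening of the visit window, at most 28/365 = 7.7% would qualify under even enrollment with no wait. To show what carry-forward would do if a 12-month percentage were computed then, assume even enrollment, no wait, blanking applied, constant hazard afterwards, recurrences recorded as they occur, and an AF-free status to carry for everyone else. With S the true 12-month AF-free share:

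- end of year 1: 91/365 + (274/365) × (1 − S)/(−ln S)
- end of year 2: half of S plus half of the year-1 value

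| True S | Year 1 | Year 2 |
|---|---|---|
| 60% | 83.7% (+23.7) | 71.9% (+11.9) |
| 75% | 90.2% (+15.2) | 82.6% (+7.6) |
| 90% | 96.2% (+6.2) | 93.1% (+3.1) |

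**6. Blanking.** If a share e of subjects recurs only in months 0 to 3, counting those episodes lowers the AF-free percentage by e. At assumed e = 5% to 15%, 70% becomes 65% to 55%. This error runs opposite to carry-forward.

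**7. Clock.** A visit at 365 ± 28 days from enrollment, after a wait of w days, falls 337 − w to 393 − w days after the procedure. With w = 30 that is day 307 to 363, always short of 365. With w = 90 it is day 247 to 303, wholly before a procedure-based window would open at day 337. The same holds for any wait above 393 − 337 = 56 days.

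**The case against.** **A rule does exist.** A reader might infer that the SAP fails to say which missing-data rule governs the endpoint, since MCAR is the initial strategy and Statistical models names neither rule. The documents do not support that. The carry-forward example is event status, so the fair criticism is the rule chosen.

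**No contradiction over censoring.** A reader might also infer that carry-forward contradicts the planned Kaplan-Meier censoring. No censoring rule is stated, so there is nothing to contradict. What stands is the bias in step 4.

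**The year-1 and year-2 figures may never be produced.** Statistical models calculates the percentage after 12 months of follow-up, and the basic report in Protocol section 13.1 comes at the end of enrollment and the end of follow-up. This stands. Section 13 does list the primary objective for analysis at both enrollment year-ends, but step 5 describes a conditional risk.

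**There may be nothing to carry.** One annual visit is planned, and the SAP says it is unknown whether subjects can have several. A lost subject may have no valid rhythm assessment after the procedure. This stands, and it is why step 3 gives upper limits.

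**Blanking and the clock are visible in intent.** Sections 9.1 and 11.2 point to exclusion of early episodes, and the natural reading of the Follow-up field is after 3 months. It would be wrong to say that blanking was forgotten. But the SAP draws recurrences from the Follow-up table as well as the Adverse Event table, and the field label does not settle by, at or after 3 months.

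**Data can still be corrected.** The SAP rules out queries during analysis, which might suggest that missing dates cannot be recovered. Its next paragraph allows reviewed corrections to be entered for later re-analyses.

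**Conclusion.** The concern holds. Applied as written, the carry-forward rule can count lost or not-yet-followed subjects as AF-free, and it biases both the primary percentage and the Kaplan-Meier estimate upward.

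At the final analysis the gap from the available-case percentage is at most L × (1 − p). That is 2.5 points at L = 10% and p = 75%, somewhat less than the sampling half-width. It is 8.0 points at L = 20% and p = 60%, well beyond it. These are differences between two calculations under assumed values, and the documents do not allow the actual size to be derived. Any 12-month percentage computed by carry-forward at the end of enrollment year 1 would be inflated, because almost no one could have reached 12 months.

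The blanking omission and the two clocks are real but secondary. They call for wording that matches the protocol's evident intent, and their size depends on early-recurrence rates and waits that are not given. The plan should be changed on all three, with carry-forward first.

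**What to change.** **SAP, Treatment of missing values.** State that carry-forward does not apply to AF recurrence.

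**SAP, Statistical models.**

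- Set time zero at the index procedure. Censor subjects without recurrence at their last rhythm assessment. Report the Kaplan-Meier AF-free estimate at 12 months with its 95% CI and numbers at risk.
- Calculate the simple percentage only among subjects with a post-blanking recurrence or an in-window annual assessment, and report how many have neither.
- State one window rule for the simple percentage. Recurrences dated after blanking and up to the end of the protocol's ±28-day window, counted from the procedure, are events. A negative visit inside that window is 12-month AF-free. The Kaplan-Meier estimate is read at 12 months.
- Report no 12-month percentage at the end of enrollment year 1.

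**Alignment.** Write the 3-month blanking period into the recurrence definitions in Protocol section 13 and the SAP, define the Follow-up field as recurrence after blanking, and reconcile the enrollment clock in Protocol section 13.1 with the procedure clock in the SAP.

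**Cost.** Wording changes and no extra visits. Recurrences in the Follow-up table must be linked to their dates in the Adverse Event table. The AF-free figure may be less favourable. The simple percentage can be slightly low, because early leavers with a recurrence stay in it and those without do not, so the Kaplan-Meier estimate belongs beside it. At the end of year 2 this effect is larger. Under the assumptions of step 5 with S = 75%, it gives 0.375/(0.500 + 0.049) = 68.3%. At that analysis, limit the simple percentage to subjects treated at least 365 + 28 = 393 days earlier, or report Kaplan-Meier alone.

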# 3. Synopsis

TITLE	Prospective observational study of pulmonary vein cryoablation in subjects with Atrial Fibrillation (AF) in Spain.	
Type of Study	Post-market non-interventional study	
Study Product Name	Arctic Front Advance® cryoballoon connected to a nitrous oxide conveying system and inserted through a steerable sheath (FlexCath Advance®) from Medtronic. The device is CE marked and will be used according to the IFU for the pulmonary vein cryoablation. In accordance with standard clinical practice, any devices available on the market at that time with the CE mark and having the indication of pulmonary vein cryoablation may also be used.	
Sponsor	Medtronic Ibérica S.A., [name] (Spain)	
Indication under investigation	Pulmonary vein cryoablation in subjects with AF	
Investigation Purpose	To reflect on standard clinical practice in pulmonary vein cryoablation in Spanish hospitals, the different procedure protocols, details of intervention, complications, long-term follow-up strategy and results in these subjects.	
Product Status	The medical device has the CE mark and will be used according to the authorized instructions for use	
Primary Objective	Evaluate the efficacy of the cryoablation procedure at 12 months, defined as the absence of recurrences of atrial fibrillation	
Secondary Objectives	
 
Description of the profile of subjects who undergo this type of procedure (demographic factors, cardiovascular risk factors, medication, physical activity, sleep apnea, alcohol, smoking, chronic pulmonary disease, obesity, etc.).
 
To evaluate the acute efficacy of the procedure: complete isolation of the pulmonary veins demonstrated by the successful electrical disconnection of the pulmonary veins in the cryoablation procedure.
 
Description of the complications related to the procedure.
 
To evaluate the use of healthcare resources which this cryoablation procedure entails.
 
 ANCILLARY Objectives The participating sites may send proposals for additional analyses over the course of the study as long as they do not interfere with the primary objectives.	

Study Design	Observational, prospective, national multicenter study			
Sample Size	The observational study plans to enroll around 1000 subjects in approximately 30 Spanish sites. The enrollment period will be 2 years plus a minimum of 1 year of follow-up, with the possibility to extend it.			

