#### 4.2. Device information

The Arctic Front Advance® connected to a nitrous oxide conveying system is used for pulmonary vein cryoablation which is inserted through a steerable sheath (FlexCath Advance®). The system progresses to the pulmonary vein ostium through a single transseptal catheterization and the balloon impacts against the venous ostium. When the nitrous oxide circulating through the system in a liquid state is released into the inside of the balloon through 8 ejectors, it leads to the switch from a very high pressure system to a very low pressure system. The sudden decompression of nitrous oxide in a liquid state means that it is transformed into a gas, causing a powerful endothermic reaction that absorbs heat from the adjacent tissues (*Joule-Thompson effect*). This reaction is the basis of the lesion caused by cryotherapy. Aerated and reheated nitrous oxide returns to the console through a connected vacuum system. For the registration of pulmonary vein potentials in real time, a circular octapolar electrode catheter (AchieveTM) is used during the ablation with an interelectrode distance of 4-6 mm (depending on the diameter of the catheter) which is inserted through the lumen of the balloon. The special configuration of the AchieveTM catheter with a rigid proximal consistency 0.9 mm diameter high supporting guidewire, can be used as a supporting guidewire for the balloon on the one hand and as a mapping and stimulation electrode on the other.

Currently at least 2 applications of cryothermia through the pulmonary vein with a duration of 180 seconds are recommended. However, you need to keep in mind that the dosing recommendations are based on data from former investigational studies of focal cryoablation. It is obvious that none of the tissue properties, the technology, or the coolants that were used are the same as those used nowadays for pulmonary vein cryoablation. This has meant that, despite the recommended application parameters, new protocols have been trialled with shorter application times and a lower number of applications per vein. The reduction in the application times of cryothermia seems to also reduce some of the complications arising from the technique such as phrenic paralysis, a circumstance which occurs more frequently after the first minute of application and during extra application after the disconnection.

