A nominal significance of a=0.05 will be assumed for a result to be considered statistically significant. The statistical analysis will be achieved using the statistical packet SPSS 20.0.

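### Predictor tests on recurrence yes/no fix no 12-month window, so with unequal follow-up a feature with no effect can look protective or harmful if its use changes over enrolment

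*SAP*

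**What the plan says.** Under Statistical models, the SAP first defines the primary result as the number and percentage free of AF recurrence after 12 months. It then adds a predictor step: "The existence of differences between patients with and without recurrence in clinical variables and patient follow-up will be explored", using Student's t for continuous and chi-squared for categorical variables. If appreciable differences appear, "logistic regression models will be proposed to study the multivariate effect of the variables and assess their predictive capacity". No window, minimum follow-up or follow-up term is stated for this step. The next paragraph plans survival tables and Kaplan-Meier for waiting times, with a search for predictive variables, but names no log-rank test or Cox model.

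Several provisions bear on whether follow-up will be equal:

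- **Timing of reports.** Protocol 13 plans analyses of the primary and secondary objectives after the first year of enrolment, "At the end of the second year of enrollment", and at the end of follow-up. It also plans two analyses of additional proposals at the end of enrolment. Protocol 13.1 lists logistic regression among the models for such proposals.
- **Length of follow-up.** Protocol 13.1 gives each subject one year from enrolment, and 9.1 has an annual visit within 28 days either way. The Synopsis, however, gives the enrolment period as "2 years plus a minimum of 1 year of follow-up, with the possibility to extend it", and 6.1 also allows an extension.
- **Closing date.** The SAP leaves this to the scientific coordinators, "so that it has been possible to collect information from 12 months of follow-up of a sufficiently large number of patients".
- **Missing status.** The SAP (Treatment of missing values) gives a subject with no event, or with no information at closing, the last valid status.
- **Source of recurrences.** The SAP draws them from both the Follow-up and Adverse Event tables. Protocol 11.2 collects recurrence after blanking as an adverse event for the whole study, so events after month 12 can enter.

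**The concern.** Recurrence yes/no is comparable between subjects only if each had the same time in which to recur. If not, late enrollees fill the no-recurrence group because they were watched for less time. Any variable that differs between early and late enrollees is then associated with recurrence through follow-up time alone.

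Change over time is plausible here. Protocol 4.2 says that "new protocols have been trialled with shorter application times and a lower number of applications per vein", and it admits future device models during the study. Protocol 13 names comparison of procedures as a possible model, and 10.2 hopes the results will help to match treatment to clinical profile. A procedure feature or clinical variable could therefore be published as a predictor when it only marks the date of enrolment.

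**Working it through.** The plan gives no recurrence rate, power or effect size, so there is no figure of its own to reproduce. The check asks how often the chi-squared test would call a feature with no effect significant.

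**Inputs from the documents.** "The sample size will be approximately 1000 subjects who must be enrolled over the two-year period" (Protocol 8.1); 3-month blanking (9.1); "A nominal significance of a=0.05 will be assumed for a result to be considered statistically significant" (13.1), taken as two-sided.

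**Assumptions not in the documents.** Enrolment is uniform over 24 months. Recurrence at 12 months is 25% (range 15% to 35%), with none counted before month 3 and a constant hazard after it. Use of the feature rises linearly from 20% to 60%.

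**Formulas.**

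- Hazard: h = −ln(1 − 0.25)/9 = 0.032 per month.
- Recurrence observed for a subject enrolled at month e with follow-up f: p(e) = 1 − exp(−h·max(f − 3, 0)).
- Use of the feature: x(e) = 0.20 + 0.40·e/24, which gives about 400 users and 600 non-users.
- Recurrence in users: p1 = mean(p·x)/mean(x). In non-users: p0 = mean(p·(1 − x))/mean(1 − x).
- Rejection probability: two-proportion z test, with pooled standard error s0 for the critical value and unpooled s1 for the distribution.

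**Worked case: month 24, all available follow-up (f = 24 − e).** Mean enrolment time is 14.0 months in users and 10.7 in non-users, so mean follow-up is 10.0 against 13.3 months. This gives:

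- p1 = 19.2% and p0 = 26.8%.
- Odds ratio = (0.1918/0.8082)/(0.2682/0.7318) = 0.65.
- Pooled rate = 0.4 × 0.1918 + 0.6 × 0.2682 = 0.2376.
- s0 = √(0.2376 × 0.7624 × (1/400 + 1/600)) = 0.0275, and s1 = 0.0267.
- Rejection probability ≈ Φ((0.0764 − 1.96 × 0.0275)/0.0267) = Φ(0.84) ≈ 80%.

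**All cases, same feature with no effect:**

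| Closing and coding | Users | Non-users | Odds ratio | Rejects (formula) | Rejects (simulation) |
|---|---|---|---|---|---|
| Month 24, uncapped | 19.2% | 26.8% | 0.65 | 80% | 80% |
| Month 24, capped at 12 months, short follow-up coded no recurrence | 14.9% | 19.1% | 0.74 | 39.5% | 39% |
| Month 30, capped, coded the same way | 22.3% | 23.6% | 0.93 | 8% | 7% |
| Month 36, extended, uncapped | 44.3% | 49.8% | 0.80 | 40% | 41% |
| Month 36, capped, 12 months for all | 25% | 25% | 1.00 | 5% | 5% |
| Month 24, closed windows only (about 500 subjects) | 25% | 25% | 1.00 | 5% | about 4–5% |

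**Direction.** With use falling from 60% to 20%, month 24 uncapped gives an odds ratio of about 1.52 and 78–79% rejections. The feature then looks harmful.

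**Sensitivity.**

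- Recurrence of 15% to 35% moves the month-24 uncapped rate from about 57% to 92%.
- Milder drift (30% to 50%) at 25% recurrence gives about 28–30% at month 24 uncapped and 13–15% at month 36 uncapped.
- Steeper drift (20% to 80%) at 20% recurrence gives an odds ratio of 0.55 and 95% at month 24 uncapped.

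**Methods that use time at risk.** On the same uncapped data the log-rank test rejects in 4–6%. In the steeper-drift simulations, Cox regression gives hazard ratios of 1.00 to 1.01 and rejects in 3–7%. With a 12-month outcome for all and visits spread over the 28-day window, logistic regression gives an odds ratio of 1.01 and 2–4% rejections.

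**The case against.** The strongest reply is that the plan, read as a whole, gives everyone the same follow-up. Protocol 13.1 sets one year per subject, the annual visit has a narrow window, and the predictor paragraph follows a primary result fixed at 12 months. The natural reading is the same 12-month classification, and logistic regression on that is legitimate. This stands in part: where every subject has 12 months and later events are not counted, there is no bias. But the SAP does not restrict the predictor step in that way. Its closing rule asks for 12 months only in enough patients, and its carry-forward rule codes the rest as free of recurrence.

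A second reply is that the documents do not place the predictor step at month 24. Predictors of recurrence are in neither the primary nor the secondary objectives, and the uncapped figures need events beyond the planned year. This also stands in part. The 80% figure is a worst case under the assumed drift; the capped 39% fits a one-year plan better. Even so, Protocol 13 and 13.1 together allow logistic models for investigator proposals at the end of enrolment.

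Third, Kaplan-Meier with a predictor search is already planned. So it would be wrong to say that the plan ignores follow-up time altogether. No test or regression for censored data is named, however, and the t, chi-squared and logistic step stands beside it.

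Fourth, the sentence speaks of clinical variables and follow-up, not procedure features, and Protocol 4.2 does not say that newer protocols will spread during enrolment. That is fair. Procedure comparisons come from Protocol 13, and the amount of drift is assumed. The mechanism applies equally to a clinical variable whose mix changes over enrolment.

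**Conclusion.** The point holds conditionally. The predictor step as written, with the carry-forward rule, permits unequal follow-up to be coded as absence of recurrence. This can occur in reports at or before the end of enrolment, with a database closed before all subjects reach 12 months, or with extended follow-up and no cap. Under the stated assumptions the false-positive rate then ranges from slight (7% at month 30 capped) to severe (about 80% at month 24 uncapped). It is about 5% with 12 months for all.

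A reader might infer that any procedure feature that changes over enrolment will falsely look protective. The documents do not support that. Rising use looks protective, falling use looks harmful, stable use is unaffected, and nothing happens when follow-up is equal. Nor do the percentages predict this registry's results, because recurrence, hazard shape and drift are all assumed.

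The analysis is exploratory and the primary percentage is not affected by the change proposed here. It should be corrected before any report on predictors of recurrence.

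**What to change.** In the SAP, Statistical models, adopt one of two rules for predictors of recurrence:

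1. Use log-rank tests and Cox regression on time to recurrence, censoring at the last rhythm information or 12 months, whichever comes first.
2. Keep logistic regression, but count only recurrences up to 12 months and include only subjects whose 12-month window has closed, with date of procedure as a covariate. Judge closure by calendar date and not by whether an event has been seen; otherwise early recurrences from open windows enter without their event-free counterparts.

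Under either rule, add to Treatment of missing values that a no-event status is not carried forward for this outcome. Rule 1 handles losses within the 12 months by censoring. Rule 2 needs a stated handling for them.

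**Cost.** SAP wording and, for rule 1, a different procedure in the same software; no new data. Rule 1 reports hazard ratios instead of odds ratios. Rule 2 uses fewer subjects in early reports: with uniform enrolment, about 1000 × 12/24 = 500 at the end of enrolment and essentially none after the first year.
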